5.3.10. Reason of Exclusion From Analysis Sets

Participants may be excluded from the analysis sets for the reasons presented in Table 2.

Table 2: Reasons for Exclusion From Analysis Sets

Analysis Set	Reason for Exclusion From Analysis Set
SPS	Not applicable
PAS	 No tafasitamab dose of No postbaseline safety assessment
ENR	No dose of any study drug
FAS	No dose of any component of study treatment
SAF	 No dose of any study drug No postbaseline safety assessment
PPS	 No dose of any component of study treatment Central pathology diagnosis different from investigator diagnosis No postbaseline ORR assessment Important Protocol deviations or other conditions that influence efficacy
PKAS	 No dose of tafasitamab No quantifiable serum tafasitamab concentration
IAS	No dose of tafasitamab No anti-tafasitamab antibody assessment

Note: If a participant has more than 1 reason for exclusion from any analysis set, then only the highest-ranking reason will be considered. For example, for the PPS, if a participant is excluded because of "no dose of any component of study treatment" and "no postbaseline response assessment," then only "no dose of any component of study treatment" will be counted when summarizing the reasons for exclusion from the PPS.

5.3.11. Withdrawal of Consent

Refer to Protocol Section 8.1 for details regarding withdrawal of consent. The date on which a participant withdraws consent will be recorded in the "End of Study/Early Follow-Up Discontinuation" eCRF.

6. BASELINE, EXPOSURE, AND DISPOSITION

Appendix A provides a list of data displays. Sample data displays are included in a separate document.

6.1. Demographics, Baseline Characteristics, and Disease History

6.1.1. Demographics and Baseline Characteristics

The following demographics and baseline characteristics will be summarized for the ENR, FAS, PAS, and SAF:

- Age (as continuous variable [years])
- Age (as categorical variable) with the following subgroups:
 - < 60 versus \geq 60 years of age
 - < 65 versus \geq 65 years of age
 - < 70 versus \geq 70 years of age
 - < 75 versus ≥ 75 years of age
- Height (cm)
- Weight (kg)
- ECOG status (categorical variable)
- Sex
- Race
- Ethnicity

Listings for demographic data will be produced for the ENR with inclusion in FAS, PAS, and SAF noted.

6.1.2. Baseline Disease Characteristics

The following baseline disease characteristics will be summarized for the FAS and PAS:

- Date of initial diagnosis of DLBCL
- Stage of DLBCL at initial diagnosis
- Current stage (Ann Arbor staging classification) and dichotomized (I and II vs III and IV)
- Diagnosis of DLBCL (NHL subtype) as per INV
- Number of prior systemic DLBCL treatment lines (categorical variable)
- Number of participants with 1 vs \geq 2 prior systemic DLBCL treatment lines
- Prior ASCT (yes vs no)
- Rituximab refractoriness (yes vs no)

- Refractoriness to last prior therapy (yes vs no)
- Relapse ≤ 12 months after initial DLBCL diagnosis (early relapse) versus relapse > 12 months after initial DLBCL diagnosis (late relapse)
- Bulky disease present versus absent (defined as having a longest lesion diameter of ≥ 7.5 cm as assessed by local radiological assessment)
- IPI Risk Group (as per IPI score/age-adjusted IPI score)
- Diagnosis of DLBCL (NHL subtype) as per central pathology
- PET result at screening
- Cell of origin by Hans Algorithm

The following coded terms (among prior anti-lymphoma surgeries/procedures) are considered prior ASCT: ASCT, SCT, AUTO SCT, autologous transplant, autologous stem cell transplant, stem cell transplant.

For PET, in case of multiple assessments at screening (eg, due to multiple lesions), the latest before Cycle 1 Day 1 will be considered.

All data for the ENR will be listed with inclusion in the PAS and FAS noted.

6.1.3. Bone Marrow Involvement at Screening/Baseline

Data on bone marrow aspiration and/or biopsies as recorded at baseline/screening or within the 4 weeks prior to the date of informed consent include the following information:

- Date and type of examination
- Type of diagnosis of DLBCL at baseline
- Bone marrow involvement by DLBCL

All summaries will include the type of examination and bone marrow involvement by DLBCL and will be presented for the PAS and FAS. All data for the ENR will be listed with inclusion in the PAS and FAS noted.

6.1.4. Definitions, Derivations, and Imputation Rules for Variables Related to Disease Characteristics

6.1.4.1. Early Versus Late Relapse After DLBCL Diagnosis

The "date of initial diagnosis of DLBCL" and the "date of first progression/relapse" can be found in the "Diagnosis of DLBCL" eCRF.

The imputation rules in Table 3 will be applied in the situation of partially completed dates.

Table 3: Imputation Rules Used to Derive the Time Between Date of Initial DLBCL Diagnosis and Date of First Progression/Relapse

Component of the Date			Variable	
DD	MMM	YYYY	Start Date	End Date
Present	Present	Present	No imputation	No imputation
Missing	Present	Present	Last day of the month	Last day of the month
Missing	Missing	Present	No imputation	No imputation
Missing	Missing	Missing	No imputation	No imputation

If the day and month are missing, and the year is present for both variables required, the participant will be assigned to the category "late relapse after initial DLBCL diagnosis" if the difference between the year for the "date of initial diagnosis of DLBCL" and the year for the "date of first progression/relapse" is 2 years or more. If the difference between the years is only 1 year, the relapse category after initial DLBCL diagnosis will be considered as "unknown." If the year is the same for both variables, the participant will be assigned to the category "early relapse after initial DLBCL diagnosis." If the relapse category cannot be determined, the participant will be assigned to the category "unknown."

6.1.4.2. Refractoriness to Prior Antilymphoma Therapies

The following 2 subgroups for treatment refractoriness in prior therapy lines will be defined using information regarding prior antilymphoma medications collected in the eCRF:

- Refractoriness to the last prior treatment line
- Rituximab refractoriness

6.1.4.2.1. Refractoriness to the Last Prior Antilymphoma Treatment Line

Refractoriness to the last prior treatment is defined as having less than a PR (ie, SD or PD) as the best overall response to the most recent therapy.

If the status for "refractoriness to the last prior treatment line" cannot be determined, the participant will be considered as having an "unknown" status.

6.1.4.2.2. Rituximab Refractoriness

Rituximab refractoriness is defined as having reached less than a PR to any rituximab-containing treatment regimen. If the status for "rituximab refractoriness" cannot be determined, the participant will be considered as having an "unknown" status.

6.1.5. Medical History and Current Medical Conditions

Medical history and current medical conditions will be summarized for the PAS and FAS by SOC, PT, and by toxicity grade according to NCI CTCAE v5.0. Coding will be performed using MedDRA v27.0 or higher.

Listings will also be provided for the ENR with inclusion in the SAF, PAS, and FAS noted.

6.2. Disposition of Participants

6.2.1. Disposition of Screened Participants

The following will be summarized for the SPS:

- Number of participants screened.
- Number and percentage of screen failures.
 - Screen failure reasons will be summarized. Percentage will be calculated based on number of participants who failed screening. A participant may fail screening due to multiple reasons.
- Number and percentage of participants enrolled.

6.2.2. Disposition of Enrolled Participants

The following summary will be provided for participants in the SPS who did not fail screening:

- Number of participants who are not screen failures.
- Number and percentage of participants who have not started treatment.
- Number and percentage of enrolled participants.
- Number and percentage of participants with ongoing treatment.
- Number and percentage of participants who completed treatment.
- Number and percentage of participants who discontinued treatment with the primary reason for discontinuation.
- Number and percentage of participants still in the study.
- Number and percentage of participants who completed the study.
- Number and percentage of participants who withdrew from the study with the primary reason for withdrawal.
- Number and percentage of participants who withdrew from the study without completing the EOS visit.
- Number and percentage of participants who withdrew from the study and completed the EOS visit.

The following summaries will be provided for the ENR:

- Number and percentage of participants by country and site.
- Number and percentage of participants who have discontinued study treatment based on components as follows:
 - Tafasitamab only, including the reason for discontinuation.
 - LEN only, including the reason for discontinuation.

- Both study drugs (at the same time or sequentially), including the reason for discontinuation, which will include LEN discontinuation as per Protocol.
- Number and percentage of participants who discontinued both tafasitamab and LEN before completing 12 cycles, including the reason for discontinuation.
- Participant disposition by cycle, including the following:
 - Number and percentage of participants who completed combination treatment (ie, Cycles 1-12 with both study drugs).
 - Number and percentage of participants who started Cycle 13 Day 1 with:
 - o Tafasitamab only.
 - o LEN only (Protocol deviation).
 - o Tafasitamab + LEN (Protocol deviation).
 - Number and percentage of participants in Cycles 1-12 who are ongoing with tafasitamab only, LEN only, or both study drugs.
 - Number and percentage of participants in Cycles 13 or later who are ongoing with tafasitamab only, LEN only (Protocol deviation), or both study drugs (Protocol deviation).
- Number and percentage of participants who discontinued tafasitamab at Cycle 13 or later, including the reason for discontinuation.

The date of last dose and reason for discontinuation of the study drugs will be in the "End of Treatment/Early Discontinuation of Treatment" eCRF. The date of EOS visit, indication if participant completed the follow-up period, and, when applicable, the reason for early follow-up discontinuation will be in the "End of Study/Early Follow-Up Discontinuation" eCRF.

In addition, the number of participants in the ENR, SAF, FAS, PAS, PPS, and will be provided. Reasons for exclusion from a set will be summarized.

Listings will be presented based on the ENR.

6.2.3. Summary Statistics of Enrollment

Summary information regarding the enrollment of participants will be provided in order to describe the maturity of data and quality of follow-up for the safety and efficacy analyses. The following will be presented for the FAS and SAF:

- Duration of enrollment period (months) = (date of last participant enrolled date of first participant enrolled + 1) / 30.4375. This will be reported for overall only.
- Date of first participant enrolled.
- Date of last participant enrolled.

6.3. Protocol Deviations

Important Protocol deviations will be identified based on reviews of the data prior to database lock.

Important Protocol deviations for the ENR will be summarized overall and tabulated according to the categories mentioned below. The number (%) of participants with at least 1 important Protocol deviation will be tabulated.

The following categories will be considered in the analysis:

- Participant enrolled and did not satisfy the entry criteria.
- Participant developed treatment discontinuation/study withdrawal criteria during the study but was not discontinued/withdrawn.
- Participant received the wrong treatment or incorrect dose.
- Participant received a prohibited concomitant treatment.
- Assessment and procedure deviation.

Listings of important Protocol deviations will be presented based on participants in the SPS who were not screen failures.

6.4. Exposure

With the exception of a summary of exposure to components of the study treatment, which will be provided for the ENR, all exposure summaries will be conducted based on the PAS, FAS, and SAF. Listings will be on the ENR with inclusion in the PAS, FAS, and SAF noted.

6.4.1. Treatment Cycles

Each treatment cycle will consist of 28 days. The treatment plan is outlined in Table 4.

Note: Each treatment cycle is 28 days.

Dose reductions of tafasitamab are not allowed during the course of the study. Unless contraindicated, tafasitamab treatment should continue even if the participant discontinues LEN.

6.4.2. Other Definitions

6.4.2.1. Duration of Exposure to Study Drug

Duration of exposure to each study drug will be calculated as

duration of exposure (months) = (date of last of dose to study drug – date of first dose of study drug + 1) / 30.4375.

6.4.2.2. Duration of Exposure to Study Treatment

Duration of exposure to the study treatment will be calculated as

duration of exposure (months) = (date of last dose of any study drug – date of first dose of any study drug + 1) / 30.4375.

6.4.2.3. Duration of Exposure to Any Study Drug

Duration of exposure to any study drug will be calculated as

duration of exposure (months) = (date of last dose of any study drug – date of first dose of any study drug + 1) / 30.4375.

6.4.2.4. Tafasitamab Infusion Rate

6.4.2.4.1. Infusion Rate

The infusion rate (per visit) will be calculated as

infusion rate (mL/h) = total volume of solution containing tafasitamab administered (mL) / total infusion time (hours).

6.4.2.4.2. Cycle Infusion Rate

For a given cycle, the infusion rate is defined as the highest infusion rate among the infusions included.

6.4.2.4.3. Standard Infusion Rate

The standard infusion rate for 12 mg/kg (Cycle 1 Days 1, 4, and 8) is defined as follows:

- 70 mL/h for the first 30 minutes
- 143 mL/h afterwards (assuming a minimum of 90 minutes)

The infusion rate upper limit will be 143 mL/h (90 minutes).

The standard infusion rate for 24 and 30 mg/kg is defined as follows:

- Cycle 1 Day 15 to Cycle 3 Day 15:
 - 62.5 mL/h (over approximately 4 hours) if the planned volume was 250 mL
 - 125 mL/h (over approximately 4 hours) if the planned volume was 500 mL
- Cycle 4 Day 1 onwards:
 - 125 mL/h (over approximately 2 hours) if the planned volume was 250 mL
 - 250 mL/h (over approximately 2 hours) if the planned volume was 500 mL

If there are interruptions or, in general, any gaps that occur with the infusion, only the actual time of infusion will be considered (ie, time gaps between infusion end and infusion restart will not be considered)

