**Table 11: Infusion Rate Modifications for Tafasitamab Infusion ( ) in Case of IRR's, Cytokine Release Syndrome (CRS)**

Infusion related reaction, Cytokine release syndrome	Infusion Rate
IRR Grade 3 and/or Grade 2 CRS during Cycle 1	If IRR Grade 3 and/or Grade 2 CRS in Cycle 1 has resolved and no further IRR Grade $\geq 3$ events are observed in cycle 2 and 3, the patient may receive tafasitamab with shorter infusion time from Cycle 4 Day 1 onward at the discretion of the investigator
IRR Grade 3 and/or Grade 2 CRS during any other Cycle	If IRR Grade 3 and/or Grade 2 CRS has resolved, tafasitamab administrations must be given at regular infusion rate i.e. approximately 4 hours in the current and subsequent Cycle. If the patient experiences no further IRR Grade $\geq 3$ , they may receive the tafasitamab administration with short infusion time from the next but one cycle onward at the discretion of the investigator.
IRR Grade 4 and/or Grade 3 CRS, Grade 4 CRS	Tafasitamab administration should be permanently discontinued.

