6.4.4.2. Over-Infusion Rate of Tafasitamab

The following will be summarized for tafasitamab in the SAF, PAS, and FAS:

- Number (%) of participants who had at least 1 infusion rate at a given visit greater than the standard infusion rate
- For each cycle, number (%) of participants who had at least 1 infusion rate among visits in a cycle greater than the standard infusion rate

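### The SAP's over-infusion summary uses limits that do not match its own average-rate metric at 12 mg/kg or protocol Table 11 from Cycle 4, and it has no tolerance

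*SAP*

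**What the plan says.** SAP section 6.4.2.4.1 reduces each visit to one number: "infusion rate (mL/h) = total volume of solution containing tafasitamab administered (mL) / total infusion time (hours"). Section 6.4.2.4.3 removes interruption gaps from the time and defines the standard rates:

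- **12 mg/kg (Cycle 1 Days 1, 4 and 8):** two steps, "70 mL/h for the first 30 minutes" and then "143 mL/h afterwards (assuming a minimum of 90 minutes"). A single limit follows: "The infusion rate upper limit will be 143 mL/h (90 minutes").
- **24 and 30 mg/kg, Cycle 1 Day 15 to Cycle 3 Day 15:** "62.5 mL/h (over approximately 4 hours) if the planned volume was 250 mL", or 125 mL/h for 500 mL.
- **24 and 30 mg/kg, Cycle 4 Day 1 onwards:** the 2-hour rate, 125 mL/h for 250 mL or 250 mL/h for 500 mL. It depends on planned volume only.

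Section 6.4.4.2 summarises "Number (%) of participants who had at least 1 infusion rate at a given visit greater than the standard infusion rate", and repeats the count by cycle. The result is planned Table 3.1.1.6.x, for the SAF, PAS and FAS.

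Protocol Table 11 covers a Grade 3 IRR and/or Grade 2 CRS in any cycle other than Cycle 1. Once the event has resolved, "tafasitamab administrations must be given at regular infusion rate i.e. approximately 4 hours in the current and subsequent Cycle". The short infusion may return from the next but one cycle, at the investigator's discretion.

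**The concern.** A count of over-infusions is useful only if each observed rate is set against a limit on the same scale and from the schedule that applied to that participant. Three features of the rule fall short of this.

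1. At 12 mg/kg an average over the whole infusion is tested against the rate of the faster step.
2. From Cycle 4 the SAP has no branch for participants who are in a Table 11 restricted period.
3. The 4-hour duration is stated as approximate, but the flag is a strict inequality with no tolerance, and one exceedance is enough to count a participant.

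The first two let a raised rate pass; the third flags trivial differences. Table 3.1.1.6.x could therefore understate some departures and be inflated by others, and a reader could not separate the two from the table alone.

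**Working it through.** **Inputs.** Rates, durations and 24/30 mg/kg volumes are from SAP 6.4.2.4.3, the metric from 6.4.2.4.1, the flag rule from 6.4.4.2, and the restriction from protocol Table 11. The 12 mg/kg bag volume is not stated; 250 mL is an assumption, supported by the first calculation.

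**Reproducing the SAP's figures**

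- Stepped schedule: 70 × 0.5 + 143 × 1.5 = 35 + 214.5 = 249.5 mL in 2 hours.
- Second step from a 250 mL bag: (250 − 35) / 1.5 = 143.3 mL/h. So 143 mL/h reproduces as the second-step rate, and the 90 minutes as that step's duration.
- It does not reproduce as a whole-infusion figure: 250 mL in 90 minutes is 250 / 1.5 = 166.7 mL/h.
- The 24/30 mg/kg limits do reproduce as whole-infusion averages: 62.5 × 4 = 250, 125 × 4 = 500, 125 × 2 = 250, 250 × 2 = 500 mL. The scale mismatch is confined to 12 mg/kg.

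**1. 12 mg/kg**

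- Schedule average: 249.5 / 2 = 124.75 mL/h.
- Infusion at 143 mL/h throughout: 250 / 143 = 1.748 h = 104.9 minutes. Its average is exactly 143, which is not greater than 143, so no flag.
- Excess over the schedule average: 143 / 124.75 = 1.146, about 15%.
- Other volumes V: schedule average = V / (0.5 + (V − 35) / 143). This gives 104.8 mL/h at 100 mL and 133.3 at 500 mL. It stays below 143 for any volume, because part of the infusion runs at 70.
- With the slow start kept, the second step could run at (250 − 35) / (1.748 − 0.5) = 172 mL/h before the average exceeded 143.

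**2. Cycle 4 onwards**

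| Cycle of event | Cycles restricted by Table 11 | SAP limit in those cycles |
|---|---|---|
| 2 | 2 and 3 | 4-hour rate in both |
| 3 | 3 and 4 | 4-hour rate, then 2-hour rate |
| 4 or later | that cycle and the next | 2-hour rate in both |

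A 2-hour infusion runs at 250 / 2 = 125 mL/h (or 500 / 2 = 250). That equals the SAP limit and is twice the 4-hour rate of 62.5 (or 125). The gap arises only for events in Cycle 3 or later.

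**3. Cycle 1 Day 15 to Cycle 3 Day 15, 250 mL**

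- 240 minutes: 62.50 mL/h, not flagged.
- 239 minutes: 250 / (239/60) = 62.76 mL/h, flagged. For 500 mL: 125.52 against 125, flagged.

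The protocol's schedule of assessments has five visits in this span (C1D15, C2D1, C2D15, C3D1, C3D15). If a fraction q of infusions at planned volume ends before 240 minutes, independently, the share of participants with at least one flag is 1 − (1 − q)^5:

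| q (assumed) | Participants flagged |
|---|---|
| 5% | 23% |
| 10% | 41% |
| 25% | 76% |
| 50% | 97% |

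The documents do not give q.

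**The case against.** The strongest reply is that 143 mL/h is a deliberate cap, labelled as an upper limit and kept apart from the stepped standard. That may have been the intention. But a cap on the step rate cannot be verified from a whole-visit average, as the 172 mL/h figure shows.

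A second reply is that the protocol's infusion-duration guidance is redacted and rate details are left to the drug handling manual, so a tolerance may exist there. It may, but the SAP's flag rule refers to none.

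Other objections stand and limit the point. A reader might infer more than the documents support in four ways:

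- **That the rule is blind to these infusions.** The same strict inequality works both ways. A 2-hour infusion that ends at 119 minutes averages 126.1 mL/h and is flagged; a 250 mL infusion without a slow start that ends at 104 minutes averages 144.2 and is flagged. What is missing is identification against the right comparator.
- **That nearly all participants would be flagged.** The 97% needs half of all infusions to end early, and independence. An infusion of 240 minutes or longer at planned volume is not flagged, and protocol section 7.1.1 lets investigators infuse more slowly.
- **That a corrected limit would reveal an omitted slow start.** A constant 124 mL/h (250 mL in about 121 minutes) would still pass a limit of 125.
- **That the IRR and CRS results depend on this table.** They are tabulated separately. The dose administration listing, the infusion-related AE listing and the review of important deviations may also bring individual cases to light.

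**Conclusion.** The point holds in a limited form. At 12 mg/kg the comparator is the second-step rate, about 15% above the average of the SAP's own schedule for an assumed 250 mL bag, and above that average for any volume. From Cycle 4 the SAP comparator and protocol Table 11 differ by a factor of two for participants in a restricted period after an event in Cycle 3 or later; the two sections must be reconciled. Before Cycle 4 an approximate duration is applied as an exact limit, with an unknown share of participants flagged as a result.

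The first two findings follow from the stated rules; only the 15% uses the assumed bag volume. The 23% to 97% range is illustrative and depends on assumed early-ending rates and independence. The consequence is misclassification in one descriptive exposure table. The primary TEAE estimand, the IRR and CRS tables and the DSMC criteria are unaffected.

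**What to change.** In SAP sections 6.4.2.4.3 and 6.4.4.2:

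1. Compare the 12 mg/kg average with the average of the SAP's two-step schedule, computed for the actual planned volume.
2. Apply one stated tolerance to every comparator, including 12 mg/kg. Without it, a correctly stepped 250 mL infusion that ends at 119 minutes (126.1 mL/h) would be newly flagged. For example, 10% gives 124.75 × 1.10 = 137.2 mL/h for 250 mL, which still flags 143 throughout. It gives 62.5 × 1.10 = 68.75 mL/h for the 4-hour infusion, about 218 minutes. If the 12 mg/kg volume is much larger, the tolerance should be checked again: at 500 mL, 133.3 × 1.10 = 146.6, which exceeds 143.
3. Reconcile the comparator from Cycle 4 Day 1 with protocol Table 11 for participants in a restricted period. This concerns the analysis comparator only, not the infusion rule.
4. State that the table detects an excess average rate and cannot show step order, and so cannot show whether the slow start was given.

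The cost is SAP wording and programming. Infusion volumes and times are already needed for the metric, and IRR and CRS grades are already collected. The downside is that the tolerance is a convention and small exceedances are no longer counted.
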